The minimum clinically important difference in successful intubation on the first attempt that would be needed to justify routine use of a video laryngoscope rather than a direct laryngoscope in the ED and ICU is uncertain. The current trial is designed to detect a 5% absolute difference between groups in the incidence of successful intubation on the first attempt. An absolute difference of 5% in successful intubation on the first attempt is similar to or smaller than the difference used in the design of prior airway management trials and is considered by airway management experts to be clinically meaningful. 21,28,38,39 Assuming (1) an incidence of successful intubation on the first attempt of 80% in the direct laryngoscope group, (2) 90% statistical power, (3) a two-sided alpha of 0.05, and (4) enrollment at 16 sites with an intra-cluster correlation for the primary outcome of 0.05, we calculated that detecting a 5% absolute increase in the incidence of successful intubation on the first attempt would require enrollment of 1,920 patients (960 per group). Anticipating missing data for up to 4% of enrolled patients, we will plan to enroll a total of 2,000 patients (1,000 per group).

Data and Safety Monitoring Board (DSMB) and Interim Analysis

A DSMB composed of experts with backgrounds in emergency medicine, pulmonary and critical care medicine, anesthesiology, bioethics, and biostatistics has overseen the design of the trial and is monitoring its conduct. The DSMB will review a single interim analysis prepared by the study biostatistician at the anticipated halfway point of the trial, after enrollment of 1,000 patients. The stopping boundary for efficacy was pre-specified as a P-value of 0.001 or less, using a chi-square test, for the difference in the incidence of the primary outcome between groups. This conservative Haybittle—Peto boundary was selected to allow the final analysis to be performed using an unchanged level of significance (P < 0.05). The DSMB retains the authority to stop the trial at any point, request additional data or interim analyses, or request modifications of the study protocol to protect patient safety. Trial safety monitoring and handling of adverse

events are described in detail in the supplementary file, section 5. Patient privacy and data storage details are listed in the supplementary file, section 6.

Statistical Analysis Principles

Analyses will be conducted following reproducible research principles using R (R Foundation for Statistical Computing, Vienna, Austria).⁴⁰ We will present summary tabulations by treatment group. For categorical variables, the number and proportion of patients will be presented. For continuous variables, the mean and standard deviation or median and interquartile range will be presented, as appropriate.

We will analyze a single pre-specified primary outcome and a single pre-specified secondary outcome using a chi-square test. Consistent with recommendations of the Food and Drug Administration⁴¹ and the European Medicines Agency⁴², each will be tested using a two-sided P value with a significance level of 0.05. The primary analysis will occur in an intent-to-treat fashion among all patients randomized, excluding only those patients whose data was withdrawn from the study. For all other analyses except safety analyses, emphasis will be placed on the estimate of effect size with 95% confidence intervals, as recommended by the *International Committee of Medical Journal Editors*⁴³, and no corrections for multiple comparisons will be performed.

Main Analysis of the Primary Outcome

The main analysis will be an unadjusted, intention-to-treat comparison of successful intubation on the first attempt between patients randomized to the video laryngoscope group and patients randomized to the direct laryngoscope group, using a chi-square test. The difference in proportions, the associated 95% confidence interval, and a p value for the primary outcome will be presented.

Secondary Analyses of the Primary Outcome

Multivariable modeling to account for covariates

To account for relevant covariates, we will develop a generalized linear mixed effects model using a logit link function with the primary outcome as the dependent variable, study site as a random effect, and fixed effects of study group and the following pre-specified baseline covariates: age, sex, body-mass index, operator experience quantified as the operator's total number of prior intubations, and location of intubation (ED vs ICU). All continuous variables will be modeled assuming a nonlinear relationship to the outcome using restricted cubic splines with between 3 and 5 knots.

Effect Modification

We will examine whether pre-specified baseline variables modify the effect of study group assignment (video laryngoscope vs direct laryngoscope) on the primary outcome using a formal test of statistical interaction in a generalized linear mixed effects model with the primary outcome as the dependent variable, study site as a random effect, and fixed effects of study group, the pre-specified proposed effect modifier, and the interaction between the two. For categorical variables, we will present the odds ratio and 95% confidence intervals within each pre-specified subgroup. Continuous variables will not be dichotomized for analysis of effect modification but may be dichotomized for data presentation. In accordance with the Instrument for assessing the Credibility of Effect Modification Analyses (ICEMAN) recommendations⁴⁴, we have prespecified the following limited number of baseline variables as potential effect modifiers and the hypothesized direction of effect modification for each:

- Patient location (ED vs ICU). We hypothesize that patient location will not modify the effect of study group assignment on the primary outcome.
- 2. Traumatic injury (Yes vs No). We hypothesize that traumatic injury will modify the effect of study group assignment on the primary outcome, with a greater increase in the

- incidence of successful intubation on the first attempt with use of a video laryngoscope compared with a direct laryngoscope among patients with traumatic injury compared to patients without traumatic injury.
- 3. Body mass index (kg/m²). We hypothesize that body mass index will modify the effect of study group assignment on the primary outcome, with a greater increase in the incidence of successful intubation on the first attempt with use of a video laryngoscope compared with a direct laryngoscope among patients with higher body mass index as compared to patients with lower body mass index. This hypothesis of effect modification is supported by a non-significant trend toward effect modification in a meta-analysis of multiple prior randomized trials.⁹
- 4. Operator's pre-enrollment assessment of the anticipated difficulty of intubation (Easy; Moderate; Difficult; Not Recorded). We hypothesize that the operator's pre-enrollment assessment will modify the effect of study group assignment on the primary outcome, with a greater increase in the incidence of successful intubation on the first attempt with use of a video laryngoscope compared with a direct laryngoscope among patients assessed as Difficult or Moderate compared to Easy. This hypothesis of effect modification is supported by significant effect modification in a meta-analysis of multiple prior randomized trials.⁹
- 5. Operator experience at the time of enrollment.
 - 1. Total number of previous intubations performed by operator. We hypothesize that the total number of previous intubations performed by the operator will modify the effect of study group assignment on the primary outcome, with a greater increase in the incidence of successful intubation on the first attempt with use of a video laryngoscope compared with a direct laryngoscope among operators with fewer previous intubations compared to operators with a greater number of previous intubations. This hypothesis of effect modification is supported by significant

effect modification observed in a prior randomized trial among critically ill adults, but differs from a meta-analysis including trials of intubation in the operating room that did not observe effect modification based on the operator's prior experience. 9,28

2. Proportion of previous intubations performed by the operator using a direct laryngoscope. We hypothesize that the proportion of previous intubations performed by the operator using a direct laryngoscope will modify the effect of study group assignment on the primary outcome, with a greater increase in the incidence of successful intubation on the first attempt with use of a video laryngoscope compared with a direct laryngoscope among operators with a lower proportion of previous intubations performed by the operator using a direct laryngoscope compared to operators with a higher proportion of previous intubations performed by the operator using a direct laryngoscope.

We will also perform an effect modification analysis for the primary outcome that includes a three-way interaction between study group, total number of previous intubations performed by the operator, and proportion of previous intubations performed by the operator using a direct laryngoscope.

Sensitivity Analyses of the Primary Outcome

We will assess the robustness of the findings of the primary analysis in a number of sensitivity analyses. First, because operators may choose to deviate from the assigned laryngoscope for the safety of the patient, we will repeat the primary analysis, but will consider patients for whom the operator crossed over on the first attempt from the assigned laryngoscope type to the non-assigned laryngoscope type not to have experienced successful intubation on the first attempt. Second, we will repeat the primary analysis among only patients

for whom data on the primary outcome from the independent observer is available (i.e., excluding cases in which operator self-report was the sole source of information for the primary outcome). Third, because the operator's prior experience with each type of laryngoscope may affect the likelihood of success with a video laryngoscope compared with a direct laryngoscope, we will repeat the primary analysis among only cases in which the proportion of prior intubations the operator has performed using a direct laryngoscope is between 0.25 and 0.75.

Analysis of the Secondary Outcome

For the secondary outcome, severe complications occurring between induction and 2 minutes following intubation, we will perform an unadjusted, intention-to-treat comparison of patients randomized to the video laryngoscope group versus patients randomized to the direct laryngoscope group, using a chi-square test.

Analyses of Exploratory Outcomes

For all pre-specified exploratory outcomes, we will conduct unadjusted, intention-to-treat analyses comparing patients randomized to the video laryngoscope group versus patients randomized to the direct laryngoscope group. We will calculate absolute risk differences or differences in medians between groups with the associated 95% confidence intervals.

Handling of Missing Data

We anticipate that no data on the primary outcome will be missing. When data are missing for the secondary or exploratory outcomes, we will perform complete-case analysis, excluding cases where the data for the analyzed outcome are missing. There will be no imputation of missing data for these outcomes. In adjusted analyses, missing data for covariates will be imputed using multiple imputations.

Trial status

The DirEct Versus VIdeo LaryngosCopE (DEVICE) trial is a prospective, multi-center, non-blinded randomized clinical trial comparing use of a video laryngoscope to use of a direct laryngoscope for the first attempt at tracheal intubation of critically ill adults in the ED and ICU. Patient enrollment began on 16 March 2022 and is being conducted in 6 EDs and 10 ICUs in the United States.

Ethics and Dissemination

Waiver of Informed Consent

Critically ill patients undergoing tracheal intubation in the ED or ICU are at significant risk for morbidity and mortality from their underlying illness. Most patients undergoing tracheal intubation in routine clinical care are intubated using either a video laryngoscope or a direct laryngoscope on the first attempt. Any benefits or risks of these two approaches are experienced by patients undergoing tracheal intubation in clinical care, outside the context of research. As a requirement for enrollment in the DEVICE trial, the patient's treating clinician must believe that either a video laryngoscope or a direct laryngoscope would be a safe and reasonable approach for the patient (otherwise the patient is excluded). Therefore, making the decision between the two approaches randomly (by study group assignment) rather than by a clinician who thinks either approach is safe and reasonable for the patient is expected to pose no more than minimal additional risk.

Obtaining informed consent for participation in the study would be impracticable. The majority of patients undergoing emergency tracheal intubation lack decisional capacity due to their underlying critical illness and surrogate decision makers are frequently absent. Further, emergency tracheal intubation is a time-sensitive procedure with only minutes between the decision to perform intubation and the completion of the procedure. Meaningful informed consent could not be executed in this brief window and attempting to obtain informed consent

would lead to potentially deleterious and unethical delays in intubation which would increase the risk of hypoxemia, hypotension, and periprocedural cardiac arrest.

Because the study involves minimal incremental risk, the study would not adversely affect the welfare or privacy rights of the participant, and obtaining informed consent would be impracticable, a waiver of informed consent was requested from and approved by the single institutional review board at Vanderbilt University Medical Center (reference number 211272). This is consistent with previous randomized trials comparing alternative approaches to tracheal intubation commonly used in clinical care. ^{28,38,39,45–50} This approach was approved by the US Department of Defense (DoD) Defense Health Agency Human Research Protection Office (EIRB# 944893).

Information for Patients and Families

Information regarding the study is made available to patients and families using a patient and family information sheet. The patient and family information sheet contains information on the purpose of the trial, study procedures, risks and discomforts, benefits, use of protected health information, confidentiality, and investigator contact information. The Defense Health Agency Human Research Protection Office determined that this procedure meets the requirements of 32 CFR 219 and DODI 3216.02_AFI40-402. At centers with a significant population of non-English speaking patients, the patient and family information sheet has been translated into Spanish and Somali languages and is made available to those patients.

Protocol Changes

Any further amendments to the protocol will be recorded on ClinicalTrials.gov as per SPIRIT guidelines. See the supplementary file, section 7, for details on how protocol changes will be handled.

Dissemination Plan

Trial results will be submitted to a peer-reviewed journal and will be presented at one or more scientific conferences.

Authors' Contributions

Approved the final version of this manuscript and critical revision of the manuscript for important intellectual content: all authors. Study concept and design: MEP, BED, SAT, SGS, BJL, DRG, WHS, TWR, AAG, JDC, MWS. Acquisition of data: all authors. Drafting of the manuscript and study supervision: MEP, BED, SAT, JDC, MWS.

Competing Interests

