5.3 Enrollment and Randomization

All patients requiring emergency tracheal intubation in a participating ED or ICU will be screened for eligibility for the DEVICE trial using the eligibility criteria in Section 3. Patients who do not meet inclusion criteria will be considered 'ineligible.' Patients who meet inclusion criteria but also meet at least one exclusion criterion will be considered 'excluded.' For patients who meet inclusion criteria but are not enrolled, the reason for exclusion will be recorded.

At enrollment, patients will be randomized in a 1:1 ratio to undergo intubation using a video laryngoscope or a direct laryngoscope using randomly permuted blocks of variable size. The randomization will be stratified by study site (each participating ED and ICU will comprise a different stratum). The study group assignments will be placed in opaque randomization envelopes, which will be located within participating units. Study group assignment will remain concealed to study personnel and treating clinicians until after the decision has been made to enroll the patient in the study.

To facilitate rapid enrollment during this time-sensitive procedure, sequentially numbered randomization envelopes will be located adjacent to the equipment required for emergency tracheal intubation (i.e., airway equipment cart, ICU work room). When the need for emergency tracheal intubation is recognized, envelopes will be obtained by the treating clinician performing the intubation (referred to as the "operator") or by a delegate while the operator sets up the equipment required for intubation. Inclusion and exclusion criteria will be posted with randomization envelopes and printed on the outside of enrollment envelopes. As the operator sets up the equipment for emergency tracheal intubation, a verbal "pre-procedural time-out" (described below) will be performed. Based on the experience from our 8 prior randomized clinical trials using the same process to perform randomization and group assignment during emergency tracheal intubation, all enrollment procedures can be completed

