9.4.1 Primary Analysis

Main analysis of the primary outcome. The primary analysis will be an intention-to-treat comparison of patients randomized to the video laryngoscope group versus patients randomized to the direct laryngoscope group with regard to the primary outcome of successful intubation on the first attempt. The difference in proportion and the associated 95% confidence interval will be presented. Between group differences will be examined using a Chi-square test.

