9.4.5 Interim Analysis

The DSMB will conduct a single interim analysis for efficacy at the anticipated halfway point of the trial, after enrollment of 1,000 patients. The stopping boundary for efficacy will be met if the P value for the difference in the primary outcome (successful intubation on the first attempt) between groups using a Chi-square test is 0.001 or less. Using this conservative Haybittle–Peto boundary ($P \le 0.001$) will allow the final analysis to be performed using an unchanged level of significance.

The DSMB will reserve the right to stop the trial at any point, request additional data or interim analyses, or request modifications of the study protocol as required to protect patient safety.

At the interim analysis, the DSMB will evaluate the rate of the primary outcome in the direct laryngoscope group. If the rate of the primary outcome in the direct laryngoscope group differs substantially from the original estimate of 80.0%, the DSMB may suggest that the investigators perform a sample size re-estimation to maintain adequate statistical power to detect the planned relative risk difference in the primary outcome between groups.

10 Privacy and Confidentiality

All patients will be assigned a unique study ID number for use in the coded study database. Study personnel will access patients' electronic health records at three planned time points: immediately following enrollment; when collecting baseline demographics and comorbidities (may occur anytime between enrollment and final data collection); and when collecting clinical outcomes (any time after the first of discharge or 28 days following intubation). The electronic health record may be accessed again, as needed, between enrollment and study publication to respond to queries from the coordinating center focused on ensuring data completeness and quality. The minimal PHI that is collected will be visible only to site investigators at the site where the patient was enrolled. The dataset for analysis will contain the unique study ID and no other patient identifiers. At the time of publication, a fully de-identified version of the database will be generated.

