Among critically ill patients undergoing orotracheal intubation in the emergency department (ED) or intensive care unit (ICU), failure to visualize the vocal cords and intubate the trachea on the first attempt is associated with an increased risk of complications. Two types of laryngoscopes are commonly available: direct laryngoscopes and video laryngoscopes. For critically ill adults undergoing emergency tracheal intubation, it remains uncertain whether use of a video laryngoscope increases the incidence of successful intubation on the first attempt compared with use of a direct laryngoscope.

Methods and Analysis:

The DirEct Versus VIdeo LaryngosCopE (DEVICE) trial is a prospective, multi-center, non-blinded, randomized trial being conducted in 6 EDs and 10 ICUs in the United States. The trial plans to enroll up to 2,000 critically ill adults undergoing orotracheal intubation with a laryngoscope. Eligible patients are randomized 1:1 to the use of a video laryngoscope or a direct laryngoscope for the first intubation attempt. The primary outcome is successful intubation on the first attempt. The secondary outcome is the incidence of severe complications between induction and 2 minutes after intubation, defined as the occurrence of one or more of the following: severe hypoxemia (lowest oxygen saturation < 80%); severe hypotension (systolic blood pressure < 65 mm Hg or new or increased vasopressor administration); cardiac arrest; or death. Enrollment began on March 16, 2022 and is expected to be completed in 2023.

Ethics and Dissemination:

The trial protocol was approved with waiver of informed consent by the single institutional review board at Vanderbilt University Medical Center and the Human Research Protection

Office of the Department of Defense. The results will be presented at scientific conferences and submitted for publication in a peer-reviewed journal.

Trial Registration

ClinicalTrials.gov registration (NCT05239195) on February 14, 2022, prior to the enrollment of the first patient.

Strengths and Limitations of this Study

- This protocol describes in detail the design and methods for a large, pragmatic trial of laryngoscope type for the emergency tracheal intubation of critically ill adults.
- Conduct in the emergency departments and intensive care units of multiple centers
 among operators with diverse prior experience with tracheal intubation, as well as broad

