Patient and Public Involvement

Materials used to communicate details of the study with patients and family members were developed with input from the Vanderbilt Community Advisory Council. Study authors will disseminate the results of this study online and via social media in forms suitable for public understanding.

Study Design

The DirEct Versus VIdeo LaryngosCopE (DEVICE) trial is a pragmatic, multicenter, unblinded, parallel-group, randomized trial comparing use of a video laryngoscope to use of a direct laryngoscope for the first attempt at emergency tracheal intubation among critically ill adults in the ED and ICU. The primary outcome is successful intubation on the first attempt. An

independent data and safety monitoring board (DSMB) is monitoring the progress and safety of the trial. Study institutions and investigators are listed in the supplementary file, section 2.

Study Population

The inclusion criteria for this study are:

- 1. Patient is located in a participating unit
- 2. Planned procedure is orotracheal intubation using a laryngoscope.
- 3. Planned operator is a clinician expected to routinely perform tracheal intubation in the participating unit.

The exclusion criteria for the study are:

- 1. Patient is known to be less than 18 years old
- 2. Patient is known to be pregnant.
- 3. Patient is known to be a prisoner.
- 4. Immediate need for tracheal intubation precludes safe performance of study procedures.
- Operator has determined that use of a video laryngoscope or use of a direct laryngoscope is required or contraindicated for the optimal care of the patient.

Randomization and Treatment Allocation

Patients are randomized in a 1:1 ratio to undergo intubation using a video laryngoscope or using a direct laryngoscope for the first attempt in permuted blocks of variable size, stratified by study site. Study-group assignments are generated using a computerized randomization sequence, placed in sequentially numbered opaque envelopes, and distributed to enrolling sites. Before opening the envelope, the operator determines that the patient meets eligibility criteria, records the predicted difficulty of intubation ("easy", "moderate", or "difficult") and selects the blade shape the operator plans to use if the patient is randomized to the video laryngoscope group ("hyperangulated" or "non-hyperangulated / standard geometry"). The

Study Interventions

Video Laryngoscope Group

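### Randomisation is stratified by site, but the primary chi-square test, its risk-difference interval and the interim test ignore site: valid, but slightly conservative

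*SAP*

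**What the plan says.** **Randomisation.** Protocol 5.3: "The randomization will be stratified by study site (each participating ED and ICU will comprise a different stratum". The SAP, under Randomization and Treatment Allocation, agrees: 1:1 allocation "in permuted blocks of variable size, stratified by study site".

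**Expected site variation.** The SAP's Sample Size Estimation lists as an assumption "4) enrollment at 16 sites with an intra-cluster correlation for the primary outcome of 0.05". Protocol 9.2 makes the same assumption.

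**Primary analysis.** SAP, Main Analysis of the Primary Outcome: "The main analysis will be an unadjusted, intention-to-treat comparison of successful intubation on the first attempt", using a chi-square test and reporting the difference in proportions with its 95% interval. Protocol 9.4.1: "Between group differences will be examined using a Chi-square test". Neither mentions site.

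**Interim analysis.** Protocol 9.4.5 sets the efficacy boundary as met if the P value "between groups using a Chi-square test is 0.001 or less", after 1,000 patients. The SAP repeats this.

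**Where site does appear.** The secondary covariate-adjusted model in the SAP is a "generalized linear mixed effects model using a logit link function with the primary outcome as the dependent variable, study site as a random effect". The SAP's effect-modification models also carry a random effect for site. No stratified test or interval is specified for the primary or interim analysis.

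**The concern.** When arms are balanced within site, a site with a high success rate raises both arms about equally, so its contribution cancels in the treatment difference. A test that ignores site estimates its standard error as if that variation had not been removed. The standard error is then too large, the interval too wide, and the P value on average too high.

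The plan expects sites to differ. An ICC of 0.05 at 80% success implies a between-site variance of 0.05 × 0.80 × 0.20 = 0.008, a standard deviation of about 9 percentage points. So it pays for stratification at randomisation and does not collect the benefit in the confirmatory analysis. The models that include site do not fill the gap: the secondary model has a logit link, the subgroup results are odds ratios, and neither is specified to give a site-stratified risk difference, which is the headline estimate.

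What is at stake is precision. There is no bias and no inflation of type I error.

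**Working it through.** **Inputs from the documents.** 80% versus 85%; two-sided alpha 0.05; 90% power; 960 per group before missing data; 16 sites; ICC 0.05; interim at 1,000 patients (500 per group) with P ≤ 0.001. The documents do not show how the ICC entered the sample size, so it serves here only as the plan's own figure for between-site variation. ICCs of 0.01 and 0.10 are assumed, to show a range.

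**The plan's own sample size.** The usual formula gives n per group = [1.96√(2 × 0.825 × 0.175) + 1.2816√(0.80 × 0.20 + 0.85 × 0.15)]² / 0.05² = 1,212, not 960. Allowing for balance within site, 1,212 × 0.95 gives about 1,152. At 960 per group the simple formula gives 82.3% power. The stated 90% is therefore not reproduced; that is a separate matter which stratifying does not repair. The step 1,920 / 0.96 = 2,000 does reproduce.

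**Variance.** With balanced arms within site, the average within-site variance is p(1 − p)(1 − ICC). The true variance of the difference is thus about 0.95 times what the chi-square test assumes.

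**Formula results, ICC 0.05, 960 per group**

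- Interval half-width, unstratified: 1.96 × √((0.1600 + 0.1275)/960) = 3.39 points. Stratified: 3.392 × √0.95 = 3.31 points. The ratio is 1.026.
- True type I error of the chi-square: 2 × [1 − Φ(1.96/√0.95)] = 0.0443.
- Power, chi-square: Φ[(0.05 − 1.96√(0.28875/960)) / √(0.95 × 0.2875/960)] = 82.9%. Stratified, with the critical value also multiplied by √0.95: 84.1%.
- Chi-square sample size needed to match the stratified power: 993.3 per group, so 2 × 33.3 ≈ 67 more patients (3.5%).
- Interim: 2 × [1 − Φ(3.2905/√0.95)] = 0.00074 against a nominal 0.001.

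**Simulation.** 200,000 runs per cell, 16 sites with 60 patients per arm, beta-distributed site rates, a constant odds ratio giving 85% overall, no continuity correction:

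| ICC | Type I error, chi-square vs stratified | Power, chi-square vs stratified | Patients equivalent, by formula |
|---|---|---|---|
| 0.01 (assumed) | 0.049 (formula) vs 0.050 | 82.1% vs 82.4% | about 13 |
| 0.05 (plan) | 0.045 vs 0.050 | 82.7% vs 83.8% | about 67 |
| 0.10 (assumed) | 0.040 vs 0.050 | 83.2% vs 85.3% | about 136 |

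At ICC 0.05, interpolating simulated chi-square power (83.3% at 976 per group, 84.0% at 992) puts 83.8% near 989 per group, or about 57 patients in total. Independent repeat simulations put the chi-square type I error at 0.044–0.046.

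**Unequal sites.** With 16 sites of 20 to 300 patients and blocks of 2, 4 and 6 (all assumed), type I error is 0.045 vs 0.050 and power 82.6% vs 83.6%. The pooled and Mantel-Haenszel differences barely separate: the standard deviation of the gap between them is 0.03 points.

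**Interim, 500 per group, ICC 0.05.** The null chance of P ≤ 0.001 is 0.0007 vs 0.0009. The chance of crossing under a 5-point effect is 10.7% vs 12.1%.

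**If the treatment effect varies by site.** Assume a site-effect standard deviation of 5 points and inference to a wider population of sites. The standard error of the difference is then √(0.01688² + 0.05²/16) = 0.0210. Coverage is 2Φ(1.96 × 0.01725/0.0210) − 1 = 89.3% unstratified and 88.5% stratified.

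**The case against.** The strongest reply is that nothing is broken. Protocol and SAP agree on a simple, transparent and valid test, used at both looks, and any error is on the safe side. A site-adjusted model is already planned, so readers will see whether site alters the conclusion, and a risk difference could be derived from it. The gain is about one power point at an ICC that is only a planning assumption, and almost nothing at 0.01. Where effects vary between sites, the stratified interval covers slightly less well. Changing a primary test and a stopping statistic after enrolment began invites questions about motive.

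Most of this is true and limits how hard the point should be pressed. The ICC 0.10 row has no source in the documents and should carry no weight in grading it. Three things remain. The plan does not commit to deriving a site-stratified risk difference from any model. Under varying site effects both intervals fall well short of 95%, and the gap between them is under one point, so that scenario is no real argument for ignoring site. And the worry about motive is met by the timing and blinding of the amendment; where those cannot be assured, a sensitivity analysis does the job.

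**Conclusion.** The concern holds. The primary chi-square test, its interval and the interim test leave out the factor used to stratify randomisation. Validity is unaffected. At the plan's own ICC of 0.05, the interval is about 2.6% too wide by formula (2.2% in simulation), true type I error is 4.4–4.6%, and about one percentage point of power is lost, equivalent to some 57 to 67 patients. The interim boundary is correspondingly a little stricter than its nominal level.

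These figures assume 80% versus 85%, 960 analysed per group, near-balance within site, similar effects across sites and no continuity correction. The gain falls to about 0.2 power points at ICC 0.01. Stratifying neither restores the stated 90% power nor covers effects that truly differ between sites. The change is worth making because it is nearly free; the trial does not depend on it.

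**What to change.** - Make the primary test a Cochran-Mantel-Haenszel test stratified by the randomisation strata (each ED and ICU). State whether a continuity correction is used: the plan is silent for its chi-square, and correcting that test would lower its simulated type I error to about 0.038–0.040.
- Report the Mantel-Haenszel risk difference with a 95% interval from a variance suited to small strata, such as Sato's.
- Use the same test for the interim boundary, so that both looks rest on one statistic.
- Keep the unadjusted chi-square and difference in proportions as a supporting analysis.

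**Cost.** No new data, little programming, and a test slightly less familiar to readers. The SAP says: "Enrollment began on March 16, 2022 and is expected to be completed in 2023". The change therefore needs a short, dated amendment to both documents, made without knowledge of outcomes by group. Protocol Section 13 involves the principal investigators and an unblinded biostatistician in preparing DSMB reports, so the amendment should precede the interim report and record who had seen what. If anyone deciding on the change has already seen outcomes by group, leave the chi-square as primary and add the stratified risk difference as a sensitivity analysis.
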